## 11.2 Severity of Adverse Events

The medical assessment of clinical severity of an AE will be determined using the definitions outlined in Common Terminology Criteria for Adverse Events (CTCAE), Version 5.0 (Published November 27, 2017, by the US Department of Health and Human Services, National Institutes of Health, National Cancer Institute):

Grade 1 Mild; asymptomatic or mild symptoms; or clinical or diagnostic observations only; or intervention not indicated

Grade 2 Moderate; or minimal, local or non-invasive intervention indicated; or limiting age-appropriate instrumental activities of daily living (ADL)

Grade 3 Severe or medically significant but not immediately life-threatening; or hospitalization or prolongation of hospitalization indicated; or disabling; or limiting self-care ADL

Grade 4 Life-threatening consequences; or urgent intervention indicated

Grade 5 Death related to AE

The above grading guidelines should be used whenever possible. For AEs that cannot be graded using CTCAE, the severity should be graded using mild (Grade 1), moderate (Grade 2), severe (Grade 3), life threatening (Grade 4), and fatal (Grade 5).

Please refer to the above-referenced CTCAE document for full description of CTCAE terms and instrumental and self-care ADLs. It is important to distinguish between severe AEs and SAEs. Severity is a classification of intensity whereas an SAE is an AE that meets serious criteria, as

described in Section 11.2.2.3.

### 11.2.1 Relationship Categorization

A physician investigator must make the assessment of relationship to investigational product for each AE. The investigator should decide whether, in his or her medical judgment, there is a reasonable possibility that the event may have been caused by the investigational product. If there is no valid reason for suggesting a relationship, then the AE should be classified as “not related”.

Otherwise, the AE should be categorized per the guidelines below. The causality assessment must be documented in the source document and the eCRF (Table 3).

**Table 3: Assessment of Relationship to Investigational Product**

Relationship	Description
Not Related	
Exposure to investigational product has not occurred.
 
OR
 
The administration of investigational product and the occurrence of the AE are not reasonably related in time
 
OR
 
The AE is considered likely to be related to an etiology other than the use of the investigational product, that is, there are no facts/evidence or arguments to suggest a causal relationship to the investigational product.

Possibly Related	
The administration of the investigational product and the occurrence of the AE are reasonably related in time.
 
AND
 
The AE could not be explained equally well by factors or causes other than exposure to investigational product

Probably Related	
The administration of investigational product and the occurrence of the AE are reasonably related in time.
 
AND
 
The AE is more likely explained by exposure to investigational product than by other factors or causes.

AE = adverse event.

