### **11.3.2 Reporting to Regulatory Agency, Institutional Review Board/Ethics Committee (EC) and Site**

The Sponsor or its designee is responsible for notifying the relevant regulatory authorities and if applicable, US central institutional review board (IRB) of related, unexpected SAEs.

In addition, the Sponsor and the CRO are responsible for notifying active sites of all related, unexpected SAEs occurring during all interventional studies across the development program.

The investigator is responsible for notifying the local IRB, local ethics committee (EC), or the relevant local regulatory authority of all SAEs that occur at his/her site, as required.

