10.7.1 Adverse Events

All AEs are collected from the time that the informed consent is signed until the end of study.

The definition for an AE to be considered treatmentemergent is as follows:

- If AE start time is recorded: an AE will be considered treatmentemergent if it occurs on or after the time of first dose of investigational product and within 28 days after a subject's last dose of investigational product.
- If AE start time is not recorded: an AE will be considered treatmentemergent if it occurs on or after the date of first dose of investigational product and within 28 days after a subject's last dose of investigational product.

Additionally, an AE that occurred prior to the date of first study drug dosing and increased in severity after start of first dosing and within 28 days of a subject's last dose of investigational product will also be considered treatment-emergent. An AE that occurred prior to first study drug dose and then again after first study drug dose at the same severity is NOT considered treatment-emergent.

AE verbatim terms will be coded to a SOC and PT using MedDRA, version 24, 01 Sep 2021.

For incidence of AEs by treatment group, SOC and PT, a subject will be counted only once per SOC and PT.

For AE incidence presented as the number and percentage of subjects with a specific AE, if there is more than one occurrence of an event, the event with the worst severity or the highest rated causality category will be summarized.

Summaries of AEs by SOC and PT will be sorted alphabetically for SOC, then by descending order of frequency of PT (for AVTX-002) within each SOC (then alphabetically for ties).

Summaries of AEs by PT will be sorted by descending order of frequency of PT (for AVTX-002), then alphabetically for ties.

Missing assessments of seriousness, intensity and relationship to study drug that have been queried and remain missing, will be treated 'worst case' for presentation filtering purposes as follows:

- Missing seriousness assessment: AE will be regarded as serious.
- Missing relationship to study drug: AE will be regarded probably related to study drug, except when start date is prior to first dose of study drug (in which case the AE will be regarded not related to study drug).
- Missing intensity assessment:
 - If subject has died, AE will be regarded Grade 5 intensity.
 - If subject has not died but subject had intervention indicated for the AE, AE will be regarded Grade 4 intensity.

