 - If none of the previous conditions are met, AE will be regarded Grade 3 intensity.

The following subject listings will be provided, using the SAS:

- All AEs (including TEAEs and nonTEAEs)
- All serious AEs (including serious TEAEs and serious nonTEAEs)
- All AEs leading to death
- All AEs leading to discontinuation of study drug

An overall summary of AEs will be provided, containing the number and percentage of subjects by treatment group with:

- any AEs
- any serious AEs
- any TEAEs
- any study drug related TEAEs

- any TEAEs leading to study drug discontinuation
- any study drug related TEAEs leading to study drug discontinuation
- any TEAEs by maximum CTCAE grade (Grade 1, Grade 2, Grade 3, Grade 4, Grade 5)
- any serious TEAEs
- any study drug related serious TEAEs
- any TEAEs leading to death
- any serious TEAEs by maximum CTCAE grade (Grade 1, Grade 2, Grade 3, Grade 4, Grade 5)

The following summary tables will be provided by SOC and PT, by treatment group:

- Incidence of TEAEs
- Incidence of study drug related TEAEs
- Incidence of TEAEs leading to study drug discontinuation.
- Incidence of study drug related TEAEs leading to study drug discontinuation
- Incidence of TEAEs by maximum CTCAE grade (Grade 1, Grade 2, Grade 3, Grade 4, Grade 5)
- Incidence of serious AEs (only if incidence of serious AEs and serious TEAEs differs)
- Incidence of serious TEAEs
- Incidence of study drug related serious TEAEs
- Incidence of serious TEAEs by maximum CTCAE grade (Grade 1, Grade 2, Grade 3, Grade 4, Grade 5)

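### A stray negative in the causality table makes Possibly Related the same test as Probably Related and leaves no row for an AE that the drug and another cause explain equally well

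*Protocol*

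**What the plan says.** Protocol 11.2.1 asks the investigator to judge whether "there is a reasonable possibility that the event may have been caused by the investigational product". It then sets a threshold: "If there is no valid reason for suggesting a relationship, then the AE should be classified as" not related. Every other AE is to be placed using Table 3, which has three rows.

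- *Not Related*: there was no exposure, or the timing is not reasonable, or another etiology is likely. The last is glossed as meaning that "there are no facts/evidence or arguments to suggest a causal relationship to the investigational product".
- *Possibly Related*: the timing is reasonable, and "The AE could not be explained equally well by factors or causes other than exposure to investigational product".
- *Probably Related*: the timing is reasonable, and "The AE is more likely explained by exposure to investigational product than by other factors or causes".

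Two things depend on this rating. SAP 10.7.1 counts subjects with "any study drug related TEAEs" and tabulates drug-related TEAEs, drug-related TEAEs leading to discontinuation and drug-related serious TEAEs. It does not say which Table 3 rows count as drug-related. Protocol 11.3.2 ties notification of regulators, the central IRB where applicable, and active sites to "related, unexpected SAEs".

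The SAP also covers ratings that stay blank after query: "Missing relationship to study drug: AE will be regarded probably related to study drug", unless the AE began before the first dose.

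**The concern.** A three-level causality scale needs a middle level for events where the drug is a credible cause but not the leading one. As worded, the middle row demands that the drug be the leading explanation. The two related rows then coincide, and the case that a middle level exists to catch has no row.

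Such cases are foreseeable in this trial. Under Protocol 8.2, salmeterol stops at Day 14, and fluticasone is halved at Day 28 and stopped at Day 42. Under Protocol 11.1.1, asthma exacerbations that miss the endpoint definition are recorded as AEs, as are endpoint events that meet the SAE definition. For a respiratory AE, withdrawal of background therapy is a ready competing explanation.

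At stake are the drug-related safety tables and the identification of SAEs as related.

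**Working it through.** The plan gives no figure to reproduce, and no arithmetic applies to the wording itself. The check is logical. Take an AE with reasonable timing and some argument for the drug. Let D be how well the drug explains it and O how well other causes do. *Possibly* and *Probably Related* share the timing condition, so only their second conditions can separate them.

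| Ordering | Not Related | Possibly Related | Probably Related |
|---|---|---|---|
| D > O | No | Yes: other causes do not explain it equally well | Yes: the drug is the likelier cause |
| D = O | No: timing is plausible and there is an argument for the drug | No: other causes do explain it equally well | No: the drug is not the likelier cause |
| D < O, some evidence for the drug | Only in part: another cause is likely, but the gloss of no evidence is not met | No | No |

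1. In the first line both related rows apply, so nothing in the text tells them apart.
2. In the second line no row applies. Yet the event meets the reasonable-possibility standard of 11.2.1, which keeps the not-related label for events with no valid reason to suspect the drug.
3. With *not* removed, D = O falls under *Possibly Related* and D > O under *Probably Related*. The rows become distinct and the tie has a category.

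The effect on the SAP's counts for a tie depends on what the site does:

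- Ticked *Not Related*: the AE is left out of the drug-related tables.
- Ticked *Possibly Related* on the strength of the label: it is counted, provided that the SAP's undefined term includes that row.
- Left blank after query: it is counted as probably related, if it began on or after the first dose.

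The size can be written down but not evaluated. Let s be the share of otherwise relatable AEs that are ties, and m the share of those ties coded *Not Related*. The number of drug-related AEs then falls by the fraction s × m, which lies between 0 (m = 0) and s (m = 1). The documents give neither s nor m.

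**The case against.** A reader might infer that tie events drop out of the drug-related counts. The documents do not support that as a fact. Protocol 11.2.1 gives a site no basis for coding a tie as not related, many investigators would tick *Possibly Related* from its label, and a blank after query adds to the count. What stands is a risk of inconsistent coding. A site that follows the written definition of *Possibly Related* cannot use that row for a tie, and the SAP's rule for missing ratings does not rescue a completed *Not Related*.

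A reader might also infer that SAEs go unreported. They do not: Protocol 11.2.2.2 and 11.2.2.4 send every SAE to the CRO within 24 hours whatever its relationship, and 11.3.2 has the investigator notify the local IRB, EC or authority of all SAEs at the site, as required. The onward notification of related, unexpected SAEs does turn on relatedness, and the documents do not say that it rests on the site's rating alone. The exposure is confined to that step.

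It is fair to add that the SAP has no separate Possibly and Probably tables. If both rows count as related, confusing one with the other leaves those counts unchanged. Safety analysis is descriptive (Protocol 12.3.4, SAP 10.7), and ratings are made under blind (Protocol 9.6), so miscoding is not expected to favor an arm. These points limit the severity. They do not supply the missing category.

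**Conclusion.** The defect is confirmed as a drafting error in an operative rule: two of the three rows state in substance the same test, and the tie case has no row. AEs of that kind may be coded differently between sites, including as *Not Related*. The drug-related TEAE, discontinuation and SAE counts may therefore be too low, and some related, unexpected SAEs may not be identified as related.

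No percentage loss can be given. Any figure for s would be an assumption, and it would equal the loss only if every tie were coded *Not Related*; the true effect could be zero. The primary efficacy analysis and the all-causality AE tables do not use this rating. The conclusion rests on the literal wording of Table 3 and on there being no other definition of causality in either document. Severity: should-fix.

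**What to change.** 1. In Protocol Table 3, delete the word *not* from the second condition of the *Possibly Related* row, so that it covers an AE that causes other than the drug could explain equally well.
2. Notify sites. The letter should also say where to place an AE for which another cause is likelier but some evidence points to the drug, since deleting one word does not plainly settle that case.
3. State in SAP 10.7.1 that drug-related means *Possibly* plus *Probably Related*.
4. Before database lock, ask investigators, under blind, to re-confirm causality for all post-dose AEs against the corrected table. A query limited to AEs coded *Not Related* would be one-sided: it could only raise the counts, and ratings in the other two rows were made under the same faulty wording.

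The cost is a one-word protocol correction, a site letter, a sentence in the SAP and one query round. The downside is that somewhat more AEs may be reported as related, in both arms.

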#### 11.2.1.1 Outcome at the Time of Last Observation

The outcome at the time of last observation will be classified as:

- Recovered/resolved
- Recovered/resolved with sequelae
- Recovering/resolving
- Not recovered/not resolved
- Fatal\*
- Unknown

\*See Section 11.2.3.

### 11.2.2 Serious Adverse Events

#### 11.2.2.1 Investigational Product Safety Information

The IB is the reference document for safety information pertaining to this study. The IB is provided separately.

#### 11.2.2.2 Reporting of Serious Adverse Events

Initial and follow-up SAE reports must be completed by the investigator or designee and sent to

the CRO within 24 hours of the first awareness of an SAE. The investigator or designee must complete, sign and date the appropriate SAE form and verify the accuracy of the information against corresponding source documents. This information is to be sent to the CRO Pharmacovigilance Department by e-mail as noted below. For questions on SAE reporting, please e-mail the drug safety mailbox noted below.

#### 11.2.2.3 Serious Adverse Event Definition

An SAE is any untoward medical occurrence, whether considered to be related to investigational product or not, that at any dose:

- **Results in death.**
- **Is life-threatening.**

*NOTE: The term "life-threatening" in the definition of "serious" refers to an event in which the subject was at risk of death at the time of the event; it does not refer to an event which hypothetically might have caused death if it were more severe.*

- **Requires inpatient hospitalization or prolongation of existing hospitalization.** *NOTE: Inpatient hospitalization is defined as 24 hours in a hospital or an overnight stay. An elective hospital admission to treat a condition present before exposure to the test drug, or a hospital admission for a diagnostic evaluation of an AE, does not qualify the condition or event as an SAE. Further, an overnight stay in the hospital that is only due to transportation, organization, or accommodation problems and without medical background does not need to be considered an SAE.*
- Results in persistent or significant disability/incapacity.

- **Is a congenital anomaly.**

*NOTE: A congenital anomaly in an infant born to a mother who was exposed to the investigational product during pregnancy is an SAE. However, a newly diagnosed pregnancy in a subject that has received an investigational product is not considered an SAE unless it is suspected that the investigational product(s) interacted with a contraceptive method and led to the pregnancy.*

- **Is an important medical event.**

*NOTE: Medical and scientific judgment should be exercised in deciding whether it is appropriate to consider other situations serious, such as important medical events that may not be immediately life-threatening or result in death or hospitalization but may jeopardize the subject or may require intervention to prevent one of the other outcomes listed in the definition above. Examples of such events are intensive treatment in an emergency room or at home for allergic bronchospasm, blood dyscrasias or convulsions that do not result in hospitalization, or development of drug dependency or drug abuse.*

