#### 11.2.2.4 Serious Adverse Event Collection Time Frame

All SAEs, regardless of the relationship to study, are collected from the time the subject signs the informed consent until the End of Study/Early Termination Visit. The investigator or designee must report all SAEs promptly to CRO within 24 hours of first becoming aware of the event.

Any SAE(s), regardless of relationship to study, which occurred during the study but is not discovered by the site until after the study has been completed must be reported to CRO within 24 hours of the first awareness of the event. Please see individual study site documentation (study binder) for forms and contact details.

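### The SAE definition exempts admissions for diagnostic evaluation of an AE without limiting this to planned stays, so some unplanned overnight work-ups of post-dose AEs fall outside SAE reporting

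*Protocol*

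**What the plan says.** Protocol 11.2.2.3 lists the seriousness criteria. One is "Requires inpatient hospitalization or prolongation of existing hospitalization". The attached note fixes the threshold: "Inpatient hospitalization is defined as 24 hours in a hospital or an overnight stay". It then takes two kinds of admission out of the criterion in a single sentence. The first is "An elective hospital admission to treat a condition present before exposure to the test drug". The second follows directly: "or a hospital admission for a diagnostic evaluation of an AE, does not qualify the condition or event as an SAE". A further sentence excuses overnight stays that have only a logistical cause, and only where there is no medical reason behind them.

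Classification as an SAE drives what follows. Protocol 11.2.2.4 states: "The investigator or designee must report all SAEs promptly to CRO within 24 hours of first becoming aware of the event". Protocol 11.3.2 makes the sponsor or its designee responsible for notifying authorities "of related, unexpected SAEs", with a parallel duty towards active sites. SAP 10.7.1 builds its serious AE listing and its serious AE and serious TEAE tables from events classed as serious.

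**The concern.** The two parts of the note pull against each other. The first says that a night in hospital because of an AE is a hospitalization. The second says that it does not count if the purpose was to evaluate the AE. A subject admitted overnight without prior plan, to find the cause of a new symptom after an injection, meets the first and is removed by the second. A site can follow the protocol exactly and record the event as not serious.

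At stake are prompt reporting and consistent classification. The hospitalization criterion is useful because it is objective. Once the purpose of the admission decides the matter, two sites can class the same stay differently depending on how they describe it. Safety and tolerability is a secondary objective of the trial (Protocol 7.1.2), and the serious AE outputs are part of how it is answered.

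**Working it through.** No arithmetic applies, and the plan gives no figure to reproduce. The check is a reading of the clause and a trace of its consequences.

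**1. Scope of the exemption (Protocol 11.2.2.3).**

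| Exempted stay | Must be elective? | Condition must precede exposure? | Other limit |
|---|---|---|---|
| Treatment of an existing condition | Yes | Yes | None |
| Diagnostic evaluation of an AE | Not stated | Not stated | None |
| Logistical overnight stay | Not stated | Not stated | No medical background |

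The word *elective* and the reference to conditions present before exposure belong to the first limb. The second limb has its own article and noun and names an AE as the reason for admission. It sets no limit on planning, timing after dose or length of stay.

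**2. What the exemption does not reach.** An admission that the AE requires for treatment still meets the hospitalization criterion. Death, life-threatening event, disability, congenital anomaly and important medical event all remain as separate routes to seriousness. The affected set is therefore overnight stays made for diagnostic evaluation of an AE that meet none of these.

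**3. Trace of an event in that set.**
- 24-hour report (Protocol 11.2.2.2 and 11.2.2.4): the duty is tied to SAEs, so none is required.
- Notification (Protocol 11.3.2): the duties of the sponsor, the CRO and the investigator are all framed for SAEs, so the event falls outside them.
- Serious AE listing and tables (SAP 10.7.1): absent.
- Recovery at analysis (SAP 10.7.1): the worst-case rule treats an event as serious only when the seriousness assessment is missing. A recorded answer of not serious stands.
- General AE data (Protocol 11.1.1; SAP 10.7.1): a non-asthma event is still collected and followed to closure. If treatment-emergent, it appears in the TEAE tables, including the one by maximum CTCAE grade.

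**4. Asthma-related events.** Protocol 11.1.1 does not require an event meeting the asthma-related definition to be recorded as an AE unless it is an SAE. A diagnostic admission for such an event, classed as not serious, could therefore be missing from the AE data. For the hospitalization component of the primary endpoint, SAP 6.2.1 looks first to SAE reports and then, if none was made, to the investigator's eCRF assessment. The endpoint thus has a second source, although the case given there is a visit to the emergency room only.

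**The case against.** The strongest reply is that the protocol has a safety net. Under the important-medical-event criterion, "Medical and scientific judgment should be exercised in deciding whether it is appropriate to consider other situations serious", and the examples given there include intensive emergency-room treatment of allergic bronchospasm. Many admissions that would cause real worry could be classed as serious by that route or as life-threatening. This stands as a limit on the size of the problem. It does not close the gap: the criterion is discretionary, and its note is directed at events that may not lead to hospitalization. It does not replace an objective overnight rule.

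A second reply is that *elective* was meant to cover both limbs. That is possible, but the sentence does not say so. If it was the intent, the sentence still needs correcting.

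Four stronger readings are tempting and not supported:
- *That unplanned overnight admissions for a post-dose AE are in general not SAEs.* Admissions for treatment are not exempted, and the other criteria still apply. If an admission combines evaluation with required treatment, the treatment part keeps it serious.
- *That these events can never be notified.* Only the hospitalization route is closed; an event judged serious on another criterion is reported and notified as usual.
- *That it is an error for an event to be Grade 3 and yet not serious.* Protocol 11.2 does include "or hospitalization or prolongation of hospitalization indicated" in Grade 3, but the same section separates severity from seriousness, so such discordance is expected by design.
- *That the serious AE rate is understated by a calculable amount.* The documents give no admission rate, so any figure would rest on an invented count. The secondary safety endpoint is the incidence of AEs together with laboratory, vital-sign and examination changes, and no formal safety testing is planned (SAP 10.7).

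**Conclusion.** The point holds in a narrow form. The diagnostic-evaluation exemption in Protocol 11.2.2.3 has no limit to elective or planned admissions and contradicts the overnight rule in the same note. An unplanned overnight stay to work up a post-dose AE that meets no other seriousness criterion is therefore not an SAE. It needs no 24-hour report, falls outside SAE notification and is missing from the serious AE outputs, while a non-asthma event normally stays in the AE and TEAE data.

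The size is unknown and probably small. The conclusion assumes that sites apply the sentence as written and do not class the event as serious on another ground. It does not imply that any hypothesis test or the primary result is affected. This is a cheap improvement to safety reporting.

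**What to change.** In the hospitalization note of Protocol 11.2.2.3, either delete the diagnostic-evaluation clause or confine it to elective or pre-planned admissions for conditions present before exposure. Keep the exemptions for elective treatment of existing conditions and for purely logistical stays. An unplanned stay of 24 hours or overnight because of an AE, including for its evaluation, then counts as hospitalization. No change to the SAP is needed, since its serious AE outputs follow the recorded classification.

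The cost is one clause in an amendment or clarification letter and a few more SAE forms. Events already recorded as not serious under the present wording would need a site query, because the SAP does not reclassify them.
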